9.9 Protocol Deviations

Protocol deviation begins as soon as the survivor signs the informed consent. Deviations are defined as a departure from approved protocol schedule of events or procedures with or without IRB approval. Protocol deviations will be classified as major or minor dependent per the identifications below.

Major: A major protocol deviation is one that will have a substantive effect on the safety, rights, or well being of subjects, data integrity, or the quality of the intervention product (CT technology).

Minor: A minor protocol deviation is a deviation that does not have a substantive effect on the safety, rights, or well being of subjects, data integrity, or the quality of the intervention product (CT technology).

Below are examples of how each protocol deviation will be coded and classified:

Category	Description	Major/Minor
Eligibility Criteria	Inclusion or exclusion not met	Major
Informed Consent	Performing study related material prior to obtaining written informed consent	Major
Withdrawal or Termination	Any situation where the study treatment discontinuation criteria are met but the subject is not discontinued from the study and continues to participate	Major

Serious Adverse Event Reporting	Failure to report serious adverse events (SAEs) within 24 hours of awareness	Major
Missed Visits	Failure to attend all 5 sessions in a 7 day period of time	Minor
Out of Window Visits	Make up sessions with live instructor are not rescheduled within a 2 week timeframe	Minor

Every major or minor deviation would be carefully monitored and registered in our database. It will be used on a regular basis, starting with FPI, by the Trial Monitoring Committee (TMC) to review the protocol deviations for that reporting period.

The TMC will identify issues trending on the study. Trends that are deemed critical by the TMC will be evaluated for safety concerns.

Section 10: GENERAL CONSIDERATIONS: REGULATORY, ETHICAL, AND TRIAL OVERSIGHT

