7.1 Discontinuation of Trial Intervention

Criteria for Permanent Discontinuation of Trial Intervention

- Participant Withdrawal: Participants may voluntarily withdraw from the trial intervention at any time for any reason. This may include personal preferences, intolerable side effects, or changes in health status that make continued participation undesirable.
- Adverse Events: Participants experiencing serious or intolerable adverse events related to the trial intervention may be discontinued from further participation in the intervention. Adverse events will be carefully monitored and managed.
- Disease Progression: If a participant experiences disease progression or other significant changes in health status that render the trial intervention ineffective or inappropriate, discontinuation from the intervention may be warranted. This may include worsening of cancer symptoms, disease recurrence, or development of new medical conditions impacting intervention efficacy.

- Non-Adherence: Participants who fail to adhere to the trial intervention protocol, including non-compliance with usage instructions for the Live coaching and software, will be discontinued from further participation in the intervention.
- Ineligibility: If a participant is found to be ineligible for continued participation in the trial intervention due to newly discovered medical conditions or other factors, discontinuation from the intervention may be necessary.

Participants who discontinue trial intervention may or may not be allowed to continue the trial, depending on the specific circumstances. In some cases, participants may continue to undergo follow-up assessments and data collection even if they discontinue the intervention. This allows for the evaluation of secondary outcomes, long-term effects, and safety monitoring following discontinuation of the intervention.

Temporary Discontinuation or Interruption of Trial Intervention

- Acute Medical Events: Temporary discontinuation may be warranted in the event of acute medical events such as hospitalization, surgery, or serious adverse reactions requiring immediate medical attention.
- Non-Urgent Medical Procedures: Temporary interruption may be necessary for non-urgent medical procedures that temporarily interfere with the participant's ability to engage with the trial intervention, such as elective surgery or diagnostic procedures.

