- Serious Adverse Events: Temporary discontinuation may be indicated in the presence of serious adverse events related to the trial intervention, pending further evaluation and resolution of symptoms.
- Participant Preference: Temporary discontinuation may occur at the participant's request due to personal reasons, travel, or other temporary circumstances that interfere with intervention adherence.

During the period of temporary discontinuation or interruption of trial intervention, the following steps will be taken:

- Documentation: The reason for temporary discontinuation or interruption will be documented in the participant's trial documentation, including the date and duration of interruption.
- Participant Education: Participants will be informed of the temporary discontinuation or interruption and provided with guidance on when and how to resume the intervention, as well as any necessary precautions or restrictions.
- Continued Trial Participation: Participants may continue in the trial during the period of temporary discontinuation or interruption, depending on the nature of the event.
- Assessments: Depending on the nature and duration of the temporary discontinuation, certain trial assessments may continue as scheduled, while others may be temporarily suspended or deferred. Assessments relevant to safety monitoring or primary endpoints will be prioritized, while non-essential assessments may be postponed until the participant resumes the intervention.

Rechallenge

- Participants will be allowed to rejoin the trial if medically permitted.

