7.2 Participant Withdrawal from the Trial

1. Voluntary Withdrawal: Participants have the right to withdraw from the trial at any time for any reason without facing any consequences.
2. Inability to Continue: Participants may withdraw if they become unable to continue participating in the trial due to medical reasons, such as worsening health status, or other personal circumstances.
3. Non-compliance: Participants may be withdrawn from the trial if they fail to adhere to the study protocol or follow the instructions provided by the research team.
4. Safety Concerns: Participants may be withdrawn from the trial if there are safety concerns identified during the course of the study, such as the development of

serious adverse events or medical conditions that may compromise their well-being.

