9.1 Analysis Sets

- The analysis will include the following datasets:
 - Intent-to-Treat (ITT) set: Including all randomized survivors, regardless of their adherence with the entry criteria. This set will be used for the primary analysis of Quality of Life changes and cancer progression.
 - Per-Protocol (PP) set: Including participants who completed the trial according to the protocol without significant deviations. PP set is a subset of ITT set, excluding survivors with major protocol deviations or those who do not complete the trial. This set will be used to summarize efficacy and support sensitivity analyses.

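### Read literally, the 9.9 Withdrawal or Termination row makes a Major deviation of follow-up that 7.1 permits and the 9.2 primary estimand relies on; 7.1 and 7.2 item 3 also leave that FACT-G data unsecured

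*Protocol*

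**What the plan says.** **Protocol 9.9, Withdrawal or Termination row (coded Major):** "Any situation where the study treatment discontinuation criteria are met but the subject is not discontinued from the study and continues to participate".

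**Protocol 7.1, permanent discontinuation.** The criteria listed are voluntary withdrawal, adverse events, disease progression, non-adherence and ineligibility. All sit under a heading about stopping the intervention. A non-adherent participant, for instance, "will be discontinued from further participation in the intervention". On what happens next: "Participants who discontinue trial intervention may or may not be allowed to continue the trial, depending on the specific circumstances". Later outcome collection is allowed for some of these people but not required. The purposes given for that follow-up are secondary outcomes, long-term effects and safety; the primary endpoint is not named.

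**Protocol 7.1, temporary discontinuation.** Here there is a priority rule: "Assessments relevant to safety monitoring or primary endpoints will be prioritized". Permanent discontinuation has no counterpart.

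**Protocol 7.2 item 3.** "Participants may be withdrawn from the trial if they fail to adhere to the study protocol".

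**Protocol 9.1 and 9.2.** The ITT set holds everyone randomized and is used for the primary FACT-G analysis. Discontinuation and non-adherence are handled by a treatment policy strategy, and missing FACT-G is multiply imputed by chained equations. The per-protocol set is defined by "excluding survivors with major protocol deviations or those who do not complete the trial".

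The Combined protocol and SAP carries the same 9.9 row, the same 7.1 and 7.2 text and the same treatment policy strategy, there applied to healthcare expenditure as the primary outcome.

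**The concern.** The row begins with criteria for stopping treatment but demands removal from the study. Those are different acts. A treatment policy estimand asks what happens to people as randomized, whether or not they keep taking the intervention, so it relies on outcomes measured after stopping. A rule that counts keeping such people in the study as a Major deviation works against that estimand.

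The row does not stand alone. Section 7.1 leaves continued follow-up to circumstances it does not define, and 7.2 item 3 allows removal from the trial for non-compliance, which is one of the events the treatment policy strategy is meant to absorb. Staff could end outcome collection for people who stop and be acting within the plan. FACT-G that could have been collected would then be imputed from earlier scores and from other participants. People who stop because of progression, adverse events or poor adherence may differ from those who stay in ways the imputation model does not capture.

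**Working it through.** The point rests on comparing sections. No figure in the plan changes: 102 / (1 − 0.30) = 145.7, which rounds up to the planned 146, and this is unaffected.

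**Step 1: one participant traced through the sections.** Take someone who stops the sessions by choice and goes on completing FACT-G. Voluntary withdrawal from the intervention is the first 7.1 criterion, so a criterion is met without any judgement by staff.

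| Section | Result for this person |
|---|---|
| 7.1 | Intervention ends; continued data collection is permitted but not required |
| 9.2 | FACT-G after stopping is analysed in the assigned arm |
| 9.9 definition | A deviation is a departure from the approved schedule or procedures; permitted follow-up is not one |
| 9.9 row, read literally | Criteria met, not removed from the study: Major |

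The row conflicts with 7.1, with the 9.2 strategy and with the definition that opens 9.9.

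**Step 2: is the post-stopping FACT-G secured elsewhere?**
- 7.1, permanent stop: continuation is left open.
- 7.1, temporary stop: primary-endpoint assessments have priority, but this does not extend to permanent stops.
- 7.2 item 3: non-compliance can end trial participation.
- 9.2: says how collected data are analysed and missing data imputed; it does not require collection after stopping.

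No provision secures it.

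**Step 3: effect on the analysis sets.** ITT includes everyone randomized, so a Major code removes nobody. Major deviations are excluded from the per-protocol set, but the 9.2 per-protocol analysis already takes only people who adhered fully, so most who stop would be out anyway.

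**Step 4: effect on the 11.1 quality limits,** taking all 146 as the denominator.
- Premature discontinuation, 5%: 0.05 × 146 = 7.3; 7/146 = 4.8%, 8/146 = 5.5%. Crossed at 8.
- Major deviations other than eligibility, 10%: 0.10 × 146 = 14.6; 14/146 = 9.6%, 15/146 = 10.3%. Crossed at 15.

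A person who stops for good counts toward the 5% limit whether kept in follow-up or withdrawn. If people who stop were the only Major deviations, the 10% limit would need 15 of them, and a root cause analysis would already be due at 8. The row can decide whether either limit is crossed only with 7 or fewer such people and enough other participants with Major deviations to reach 15, that is at least 15 − 7 = 8 others. The effect is small.

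**The case against.** **The row may mean something narrower.** It ends with continuing to participate, and 7.1 uses participation mainly of the intervention. The rows of 9.9 are offered as examples under a definition that permitted follow-up does not meet. A sensible reader could take the target to be people still receiving sessions after they should have stopped. That is probably the intent, and it stands as a limit on the point: the conflict lies in the literal wording. But the row says study, and under the narrower reading the proposed rewording only states what was meant.

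**Non-adherence may seldom be declared.** Section 6.3 lets both arms stop and restart, missed sessions are Minor in 9.9, and no threshold defines non-adherence. This stands: how often that criterion would be met is unknown. The voluntary-stop case does not depend on it.

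**Stronger readings the documents do not support.**
- A reader might infer that the 11.1 limits reward losing FACT-G, since uncollected endpoint data have a looser limit (15%) than Major deviations (10%). The 5% discontinuation limit is usually reached first either way, and crossing a limit leads to a root cause analysis, not to anyone's withdrawal.
- A reader might apply the 30% drop-off of 9.7 to estimate a bias. Section 9.7 attributes that drop-off to long follow-up and spreads it evenly, from 73 to 51 in each arm. It is not a rate of stopping the intervention, and no score difference is given to go with it.
- A reader might infer that staff will withdraw people who stop. Nothing shows this; the plan allows it and, in the literal 9.9 row, points toward it.

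**Changing 7.1 and 7.2 goes beyond one table row.** It does, but correcting the row alone would leave the data the estimand relies on optional. Restricting safety withdrawals under 7.2 item 4 is not needed.

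**Conclusion.** The point holds in this form: the literal 9.9 row conflicts with 7.1 and with the 9.2 treatment policy strategy, and 7.1 with 7.2 item 3 leaves post-stopping FACT-G uncollected at staff discretion. This is more than missing detail, because stated rules work against the primary estimand. ITT membership is unchanged, and the per-protocol and quality-limit effects are small. The consequence that matters is avoidable missing FACT-G in people who stop. Its size cannot be determined from the documents, and it would arise only if staff used the discretion or followed the row as worded. The conclusion assumes that study in the row means the trial; that the intervention was intended is an inference from 7.1, not something the plan states. The change should be made, with medium confidence, mainly because it costs so little.

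**What to change.** 1. **9.9 row:** replace removal from the study with *not discontinued from the trial intervention*.
2. **7.1, permanent discontinuation:** replace the open-ended sentence on continuing with a rule. Anyone who permanently stops the intervention, for any reason, stays in scheduled remote outcome follow-up, including FACT-G, unless they withdraw consent or are unable to continue; staying in is not a deviation.
3. **7.2 item 3:** non-compliance ends the intervention, not outcome follow-up. Leave item 4 (safety) as it is.

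Cost: wording in three places. FACT-G is self-reported through the digital platform and already scheduled in 6.1 and 9.2, so there are no added participants, visits or procedures, and the sample size stays at 146.

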10.1 Regulatory and Ethical Considerations

This trial will be conducted in accordance with the protocol and with the following:

- Consensus ethical principles derived from international guidelines including the Declaration of Helsinki and Council for International Organisations of Medical Sciences (CIOMS) International Ethical Guidelines
- ICH Good Clinical Practice (GCP) Guidelines
- Applicable laws and regulations

Investigators' Responsibilities:

- Ensuring that the trial is conducted in accordance with the protocol, International Conference on Harmonisation Good Clinical Practice (ICH GCP) guidelines, and applicable regulatory requirements.
- Obtaining informed consent from all participants prior to their participation in the trial.
- Reporting all serious adverse events (SAEs) to the sponsor promptly and accurately.
- Ensuring the accuracy and completeness of all data collected during the trial.
- Complying with regulatory requirements for the conduct of clinical trials in their jurisdiction.
- Maintaining the confidentiality of participants' data and protecting their rights and well-being throughout the trial.

Sponsor's Responsibilities:

- Designing the trial protocol and ensuring it is scientifically sound and ethically appropriate.
- Obtaining regulatory approval to conduct the trial and ensuring ongoing compliance with regulatory requirements.
- Providing the necessary investigational product and ensuring its quality and supply throughout the trial.
- Monitoring the conduct of the trial to ensure compliance with the protocol, GCP guidelines, and regulatory requirements.
- Collecting, analyzing, and reporting trial data to regulatory authorities and other relevant stakeholders.
- Ensuring that all investigators are adequately trained and informed about their roles and responsibilities.
- Ensuring that appropriate insurance coverage is in place to protect participants and investigators.

- Addressing any safety concerns or protocol deviations promptly and appropriately.
- Ensuring that the trial is conducted in accordance with ethical principles and that participants' rights and well-being are protected.
- Providing financial support for the conduct of the trial, including funding for investigator fees, site costs, and other expenses.

10.2 Committees

The trial will establish an Trial Monitoring Committee (TMC) to oversee the safety and integrity of the trial. The TMC will consist of independent experts in relevant fields such as oncology, biostatistics, and cancer exercise specialists. Their primary role will be to review safety data at regular intervals during the trial to ensure participant safety.

Trial Monitoring Committee will perform safety assessments every 6 months. But they will meet more often if needed such as in case of increase in AEs. The Trial Monitoring Committee will be responsible for making a determination of continuing the study based upon results of the safety assessment.

10.3 Informed Consent Process

The informed consent process will include the following key elements:

- Explanation of the trial: Participants will be provided with detailed information about the purpose, procedures, risks, and potential benefits of the trial.
- Voluntary participation: Participants will be informed that their participation in the trial is entirely voluntary, and they have the right to withdraw at any time without penalty.
- Understanding: The information provided will be presented in a clear and understandable manner, ensuring that participants comprehend the nature of the trial and its implications for their health.

- Confidentiality: Participants will be assured that their personal information will be kept confidential to the extent allowed by law.
- Opportunity for questions: Participants will be given the opportunity to ask questions and seek clarification about any aspect of the trial before providing consent.

Rescreening:

- Participants can be rescreened. Refer section 5.6 for the details.
- Participants who undergo rescreening will not typically be required to complete a new informed consent process if their initial consent remains valid. However, this will be clearly stated in the protocol, and any specific circumstances requiring a new consent will be outlined.

10.4 Data Protection

- Confidentiality Measures: Personal data will be anonymized or pseudonymized whenever possible to protect participant identity. Only authorized personnel will have access to identifiable information, and strict confidentiality protocols will be followed.
- Secure Data Storage: Participant data will be stored securely in electronic databases with restricted access. The databases will be encrypted and password-protected to prevent unauthorized access.
- Limited Access: Only authorized personnel involved in the conduct of the trial will have access to participant data. Access will be granted based on predefined roles and responsibilities, and access logs will be maintained to track data access.
- Data Transfer: When transferring data between sites or to third-party vendors, encryption and secure file transfer protocols will be used to minimize the risk of interception or unauthorized access.
- Training and Awareness: All personnel handling participant data will receive training on data protection policies and procedures. Regular awareness campaigns will be conducted to reinforce the importance of data security.

In the event of a data security breach, the following steps will be taken:

- Immediate Response: Upon discovery of a breach, the responsible personnel will take immediate action to contain the breach and mitigate any potential harm.
- Notification: Relevant stakeholders, including participants, regulatory authorities, and ethics committees, will be promptly notified of the breach in accordance with applicable regulations and guidelines.
- Investigation: A thorough investigation will be conducted to determine the cause and extent of the breach. This may involve forensic analysis of systems and data logs.
- Remediation: Measures will be implemented to address the vulnerabilities that led to the breach, such as software patches, system updates, or changes to procedures.
- Documentation: A detailed report of the breach, including the cause, impact, and remedial actions taken, will be documented for regulatory compliance and future reference.

10.5 Trial Termination

Decision Rights of Sponsor or Designee to Terminate the Trial:

- The sponsor or designee may also terminate the trial if there are safety concerns, lack of efficacy, or other unforeseen circumstances that jeopardize the integrity of the trial or the safety of participants.
- The sponsor holds the decision-making power to suspend or terminate the trial based on recommendations from the Trial Monitoring Committee, IRB and PI.

Section 11: GENERAL CONSIDERATIONS: RISK MANAGEMENT AND QUALITY

ASSURANCE

11.1 Quality Tolerance Limits

The purpose of this section is to identify what will trigger internal quality assurance (QA) processes to ensure continuous improvement. The Trial Monitoring Committee will provide the oversight to review the following parameters in the table. The parameter thresholds will be evaluated on a monthly basis. When these thresholds have crossed, the primary QA process employed by the committee will conduct a Root Cause Analysis (RCA). These are the following steps:

1. Collect relevant data
2. Identifying the root causes
3. Find corrective solution
4. Update protocol
5. Implement changes with appropriate change management with relevant stakeholders
6. Monitor if the corrective solution works.

Critical to Quality Factor	Parameter	Definition	Justification for Parameter	Parameter Threshold
Safety reporting	Percentage or number of immediately reportable events reported late	Percentage or number of immediately reportable events (e.g., SAEs and other events as defined in the protocol) that are reported more than 1 day after awareness of the event	A high number of late reported, immediately reportable events could impact participant safety due to lack of timely awareness of emerging safety profile	5%

Eligibility criteria	Percentage or number of participants randomized who do not meet inclusion/exclusion criteria	Percentage or number of randomized participants with Protocol Deviations in inclusion/exclusion criteria	A high number of study participants not meeting the entrance criteria could have a significant impact on interpretation of the primary endpoint and overall validity of the trial results.	5%
Intervention handling and administration	Percentage or number of participants with premature discontinuation	Percentage or number of participants who discontinued treatment before the end of the treatment period as defined by protocol	A high number of participants discontinuing treatment could have a significant impact on interpretation of the primary endpoint.	5%
Withdrawal criteria and trial participant retention	Percentage or number of participants with withdrawal of informed consent	Percentage or number of participants with withdrawal of informed consent after treatment allocation	A high number of participants withdrawing informed consent may indicate excessive survivor burden and could significantly impact collection and interpretation of the	5%

			primary endpoint.	
Withdrawal criteria and trial participant retention	Percentage or number of lost to follow-up participants	Percentage or number of participants who are lost to follow-up (i.e., have not continued in the trial until the last planned safety assessment and have not revoked consent nor have been reached by investigator site personnel through normal communication methods). These participants have not completed the trial and their status is unknown	A high number of participants lost to follow-up may indicate excessive participant burden and could impact the collection and interpretation of long-term safety and efficacy data.	10%
Procedures supporting study endpoints and data integrity	Percentage or number of study participants for whom study endpoint data was not collected	Percentage or number of study participants for whom study endpoint data was not collected; this could include	A high number of study participants for whom the failure to collect study endpoint data could impact analysis and interpretation of	15%

		inability to perform study procedure at the protocol-defined time point	study results	
Procedures supporting trial endpoints and data integrity	Percentage or number of participants with "Major" protocol deviations other than eligibility	Percentage or number of participants with protocol deviations during the trial which are not related to protocol inclusion/exclusion criteria (i.e., informed consent, trial intervention, prohibited concomitant medication, trial procedures, safety reporting, and discontinuation)	A high number of study participants with important protocol deviations during the trial could have a significant impact on interpretation of the primary endpoint and overall validity of the trial results. It can also impact participant safety	10%
Procedures supporting trial endpoints and data integrity	Percentage of participants censored in the statistical analysis because they had no bills the	Percentage or number of participants who are at risk of censoring for hospital costs	High number of participants censored for primary objective analysis would translate into smaller than assumed sample	10%

	entire time		size and may impact the interpretation of the efficacy results. Alternatively, final primary objective analysis would be delayed if required sample maturity is not reached within the assumed timelines	
Randomization	Percentage or number of randomized participants who were incorrectly stratified	Percentage or number of randomized participants who were incorrectly stratified	High number of participants who were incorrectly stratified may lead to imbalances in baseline characteristics between treatment arms, introduce biases in the data, and significantly affect the outcome of a trial	10%

